Official Title: Randomized-controlled trial of an orthotic designed to equalize leg lengths for patients using a controlled ankle movement boot

NCT Number: NCT03848949

Document Date: 8/31/2020

Study Protocol:

Background and purpose

Patients with foot and ankle injuries are often made weight-bearing as tolerated (WBAT) in a controlled ankle movement (CAM) boot at some point during their recovery and rehabilitation period. While WBAT in a CAM boot, patients often experience an asymmetric gait associated with the effective leg length discrepancy between the booted extremity (longer) and the contralateral extremity with a regular shoe (shorter). This asymmetry may cause balance problems or place strain on the patient's joints resulting in back, knee, and hip pain.

An orthotic has been designed that is added to the outside of a regular shoe in order to eliminate the effective leg length discrepancy between the booted extremity and the contralateral limb. Although this specific orthotic has not been studied, some proof of concept lies in studies that show that back pain can be managed with foot orthotics. The purpose of this study is to determine if using the leg-length-evening orthotic can improve balance and/or decrease the development of pain in the lower extremities and spine for patients who are WBAT in a CAM boot.

Inclusion criteria

1. Age at least 18 years old
2. Patients who are newly made WBAT in a CAM boot for at least two weeks

Exclusion criteria

1. Patient refuses.
2. Patient is incarcerated, incapacitated, or otherwise unable to provide appropriate informed consent.

Methods

This will be a randomized-controlled study in which eligible patients will be randomized to either the leg-length-equalizing orthotic intervention group or to a control group. At the end of a two-week period of immobilization, patients will receive a phone call and will be asked the following questions:

Over these last two weeks while walking in the CAM boot:

- How would you say your balance has been when walking (where 0 is terrible balance where you are falling all the time and 10 is perfect balance where you feel completely stable)?
- How many times have you tripped or stumbled?
- How many times have you fallen to the ground?
- How much pain were you having in your knees on a scale of 0-10 (where 0 is no pain and 10 is severe pain)?
- How much pain were you having in your hips on a scale of 0-10 (where 0 is no pain and 10 is severe pain)?

- How much pain were you having in your back/spine on a scale of 0-10 (where 0 is no pain and 10 is severe pain)?

Statistical Analysis

Statistical analyses were conducted in Stata Version 16.0 ® (College Station, TX, USA). Both intention-to-treat and as-treated analyses were conducted for all comparisons. T-tests (for continuous variables), Pearson's chi-squared tests (for categorical variables with expected cell counts ≥ 5), and Fisher's exact tests (for categorical variables with expected cell counts < 5) were used to compare baseline demographics. Balance (primary outcome), pain, the numbers of trips and falls, and the number of feet walked per day were compared using the Wilcoxon rank-sum test (equivalent to the Mann-Whitney U test), as these were considered to be non-normally distributed variables. The level of significance was set at $p < 0.05$.

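### The pain aim is about the development of pain, but the data described give only pain level at two weeks, so new pain cannot be separated from prior pain or its relief

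*Combined protocol and SAP*

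**What the plan says.** - **Aim (Background and purpose).** Besides balance, the trial is to find out whether the orthotic can "decrease the development of pain in the lower extremities and spine". The rationale offered is that "some proof of concept lies in studies that show that back pain can be managed with foot orthotics".
- **Eligibility (Inclusion and Exclusion criteria).** Adults are eligible as "Patients who are newly made WBAT in a CAM boot for at least two weeks". The only exclusions are refusal and inability to consent, so prior knee, hip or back pain is no bar to entry.
- **Data (Methods).** "At the end of a two-week period of immobilization, patients will receive a phone call and will be asked the following questions". The questions are framed by "Over these last two weeks while walking in the CAM boot", and the pain items ask for a level, for example "How much pain were you having in your knees on a scale of 0-10", then the same for hips and for back/spine. None asks whether pain is new, worse or long-standing.
- **Analysis (Statistical Analysis).** Balance is named as the primary outcome. Pain is compared by an unadjusted rank-sum test, and "Both intention-to-treat and as-treated analyses were conducted for all comparisons". Baseline demographics are compared between arms, but the variables are not listed.

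**The concern.** Development of pain, in its ordinary sense, means onset. A level recalled at two weeks mixes pain that began in the boot, pain that was already there, and any lessening of that earlier pain. To call a patient's pain new, one must know whether it was present beforehand. Neither the eligibility criteria nor the described data supply that.

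Two things are at stake:

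- A lower two-week score in the orthotic arm could be reported as less development of pain when part of it is relief. The protocol's own rationale points to managing existing back pain, so this is not far-fetched.
- The as-treated comparison is not protected by randomisation. If prior pain influences who uses the orthotic, the described data offer no means of adjusting for it.

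**Working it through.** **1. Aim against data.** The aim needs each patient's pain before the boot and during it. The described data give only the second. A two-week score above 0 therefore cannot be classed as new or pre-existing.

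**2. What randomisation covers.** Prior pain is balanced between randomised arms in expectation, so the intention-to-treat difference in pain level is unbiased. The gap there concerns what the difference means and how precise it is.

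**3. How far level and onset can differ.** The documents give no pain rates, so every input here is assumed. Let any pain at two weeks be 50% in controls and 40% with the orthotic. Let *b* be prior pain prevalence, equal in both arms, and *k* the proportion of prior pain that persists.

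- New pain per randomised patient = two-week prevalence − *b* × *k*.
- Risk among patients without prior pain = that quantity ÷ (1 − *b*).

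With *k* = 1 in both arms:

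| *b* | Control risk | Orthotic risk | Ratio | Difference per randomised patient |
|---|---|---|---|---|
| 0% | 50% | 40% | 0.80 | 10 points |
| 10% | 40/90 = 44% | 30/90 = 33% | 0.75 | 10 points |
| 20% | 30/80 = 38% | 20/80 = 25% | 0.67 | 10 points |
| 30% | 20/70 = 29% | 10/70 = 14% | 0.50 | 10 points |

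So under equal persistence the absolute difference is recovered, but the per-arm rates and the ratio are not.

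Now let persistence be 1 in controls and *k* with the orthotic. The new-pain part of the 10 points is (50 − *b*) − (40 − *b* × *k*) = 10 − *b* × (1 − *k*):

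| *b* | *k* = 90% | *k* = 75% | *k* = 67% |
|---|---|---|---|
| 10% | 9 | 7.5 | 6.7 |
| 20% | 8 | 5 | 3.3 |
| 30% | 7 | 2.5 | 0 |

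If prior pain persisted more often with the orthotic than in controls, the sign reverses and the new-pain part exceeds 10. The described data cannot tell these cases apart.

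**4. As-treated comparison.** The documents give no sample size, adherence or correlation, so this too is illustration. The simulation had these features:

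- No true effect and 50 patients per arm. Latent normal scores had SD 2.5 and mean 3 or 0, rounded and truncated to 0-10.
- 20% or 30% of the orthotic arm stopped and was counted as untreated. Stopping was weighted by a multiplier per SD of prior pain, so a patient 1 SD above the mean has multiplier² times the weight of one 1 SD below (1.25² = 1.6; 1.5² = 2.3; 2.0² = 4; 2.7² = 7.3).
- *r* is the correlation of prior with two-week pain. There were 6,000 runs per cell.

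Rank-sum false-positive rate at nominal 5%:

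| Multiplier | *r* = 0.3 | *r* = 0.5 | *r* = 0.7 |
|---|---|---|---|
| 1.25 | 5% | 5-6% | 5-7% |
| 1.5 | 6% | 6-8% | 7-10% |
| 2.0 | 6-8% | 8-13% | 11-19% |
| 2.7 | 6-9% | 11-17% | 17-29% |

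At *r* of 0 to 0.1 the rate was 4-6% at every multiplier. Intention-to-treat and baseline-adjusted as-treated rates were 4-6% throughout. With only 10% stopping (latent mean 3), the rate was 5.5% at multiplier 1.5 and *r* = 0.5, and 6.8% at multiplier 2.0 and *r* = 0.7. The spurious shift for *r* of 0.3 to 0.7 was 0.03-0.2 points at multiplier 1.25 and 0.1-0.7 at 2.7.

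In this model patients with more prior pain stop, which favours the orthotic. The opposite selection would count against it. Stopping also depends only on prior pain here, so adjustment removes all the bias; in practice it would remove only the part due to prior pain.

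**5. Precision.** With a 0.5 SD latent shift and 50 per arm, gain from adjustment = ((z of adjusted power + 1.96) ÷ (z of unadjusted power + 1.96))² − 1. It is about 0% at *r* 0-0.1, 4-9% at 0.3, 15-27% at 0.5 and 44-75% at 0.7. Low *r* is plausible, because pain before the boot is a different state from pain while walking in it.

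**The case against.** **The point rests on one word.** The background section speaks of strain from uneven gait causing pain, and the questions are tied to the time in the boot. On that reading, development of pain may simply mean pain experienced in the boot, which a randomised post-only comparison answers validly. This stands in part: the level comparison is sound, and under equal persistence the absolute difference in new pain is recovered. It does not remove the ambiguity, because relief of existing pain would look the same, and the protocol's rationale is about managing existing pain.

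**Absence is not established.** Baseline variables are not listed. The analysis section also says "the number of feet walked per day were compared using the Wilcoxon rank-sum test", although no such item is among the listed questions, so the description of data is incomplete. This stands. A reader might infer that baseline pain was never collected and that new pain can never be reported. The documents support only the narrower statement that this cannot be done from the data described.

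**The as-treated issue is not specific to pain.** The rank-sum test is unadjusted for every outcome, as-treated results sit beside intention-to-treat results, and nothing in the text rests conclusions on them. This also stands and limits the weight of that part. A reader might take the upper simulated rates as the trial's likely error rate, but the documents give nothing that favours those cells over the ones near 5%.

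**Classifying new pain has its own flaw.** A zero before the boot may reflect little walking rather than a sound joint, and the two ratings have different recall frames. This stands, and it applies to new pain as much as to worse pain.

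**Conclusion.** The concern holds as a minor one, with medium confidence. The aim is worded as onset, while the data described measure level. From those data, new pain cannot be separated from pre-existing pain or from its relief, and neither analysis set can be adjusted for prior pain.

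A reader might go further and infer that the pain comparison is invalid or that the main result is compromised. The documents do not support that: randomisation keeps the intention-to-treat comparison of pain level unbiased, and the primary outcome, balance, is untouched.

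The size is unknown. In the illustrations, the new-pain share of a 10-point difference runs from all of it (equal persistence) to none (30% prior pain, 67% persistence with the orthotic). As-treated bias could go in either direction. It is small unless selection is strong and correlation moderate to high. Both statements rest wholly on assumed inputs.

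**What to change.** First confirm whether any baseline pain item was recorded.

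**If enrolment is open:**

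- Before allocation is revealed, ask for 0-10 knee, hip and back/spine pain, for example over the week before the patient began walking in the boot.
- Analyse each two-week score adjusted for its own baseline, by rank ANCOVA or proportional odds, in both analysis sets.
- Report new pain (0 at baseline, above 0 at two weeks) and worse pain by arm with 95% intervals, as descriptive only, since both compare ratings with different recall frames.

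The cost is three questions, about a minute per patient, one covariate per pain model, and an analysis slightly less simple than a rank-sum test. The new-pain estimate would be imprecise. At an assumed 50 per arm with 20% prior pain, 40 per arm remain. Then 37.5% v 25% gives SE = √(0.375 × 0.625/40 + 0.25 × 0.75/40) = 0.103, so 12.5 points with a 95% interval of about −8 to 33.

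**If data collection is complete**, as the past tense of the Statistical Analysis section suggests: use any baseline pain item that was recorded. Otherwise:

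- reword the pain aim and conclusions to pain level during two weeks in the boot;
- state that new and pre-existing pain cannot be separated;
- label the as-treated pain results as unadjusted for prior pain.

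Without a recorded baseline item this costs wording only; the downside is a narrower pain claim.

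### Balance, the primary outcome, is tested by both intention-to-treat and as-treated at 0.05, with neither ranked and as-treated undefined; the as-treated test is biased if orthotic non-use is related to balance

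*Combined protocol and SAP*

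**What the plan says.** Under Methods, "eligible patients will be randomized to either the leg-length-equalizing orthotic intervention group or to a control group". At two weeks "patients will receive a phone call and will be asked the following questions"; six questions follow, on balance, trips or stumbles, falls, and knee, hip and back pain. None asks whether the orthotic was worn.

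Under Statistical Analysis, "Balance (primary outcome), pain, the numbers of trips and falls, and the number of feet walked per day were compared using the Wilcoxon rank-sum test". The same section states "Both intention-to-treat and as-treated analyses were conducted for all comparisons", and "The level of significance was set at" 0.05. As-treated is mentioned nowhere else. The section is in the past tense: "Statistical analyses were conducted in Stata Version 16.0".

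The documents do not say which of the two analyses is primary, what follows if they disagree, what counts as orthotic use, how use is recorded, or how a control patient who obtains a lift would be classed.

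**The concern.** The statement about analysis sets covers every comparison, so it covers balance. The plan yields two p-values for its primary outcome at the same threshold and no rule for choosing between them. If one is below 0.05 and the other is not, either can be presented as the trial's result.

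The two analyses are not equally sound. Randomisation protects the intention-to-treat comparison only. As-treated sorts patients by something that happens after randomisation, and an unadjusted rank-sum test cannot correct for it. The device is worn on the shoe while walking, so how steady a patient feels could plausibly affect whether they keep wearing it. If patients with poorer balance stop and are counted as control, the as-treated test shows a benefit that is not there. If patients with better balance stop, it understates a real one.

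**Working it through.** **No plan figure to reproduce.** The only design number in the documents is the 0.05 level. Sample size, SD, effect size and non-use rate are not given, so everything below except that level is an assumption.

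**1. Simple multiplicity.** If a win on either test counts, the ceiling for two independent tests is 1 − 0.95² = 9.75%. The two analyses share most of their patients, so the true figure is lower (step 3).

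**2. Closed-form bias with no true effect.** Let balance have SD σ, let a proportion q of the orthotic arm not use it, and let non-use be set by a normal latent variable with correlation ρ to poorer balance. Allocation is 1:1, and non-users are moved to control. With φ the normal density at the q-quantile:

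- non-users' mean shift = −ρσφ/q
- users' mean shift = +ρσφ/(1 − q)
- enlarged control group's mean shift = −ρσφ/(1 + q)
- as-treated difference = ρσφ × [1/(1 − q) + 1/(1 + q)] = 2ρσφ/(1 − q²)

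For σ = 2, q = 0.30, ρ = 0.3 and φ = 0.348: 2 × 0.3 × 2 × 0.348 / 0.91 = **0.46 points**, with no treatment effect at all. The observable correlation between non-use and balance is only ρφ/√[q(1 − q)] = 0.3 × 0.348 / 0.458 = 0.23, so a weak link is enough.

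**3. Simulated false-positive rates.** Balance was normal with mean 7 and SD 2, rounded and limited to 0–10. There were 50 per arm, non-use in the orthotic arm only, two-sided tie-corrected rank-sum tests, and 10,000 replicates per cell.

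| Non-use in the orthotic arm | 5% | 10% | 20% | 30% |
|---|---|---|---|---|
| As-treated, ρ = 0.3 | 6.1% | 7.6% | 12.7% | 17.9% |
| As-treated, ρ = 0.5 | 7.5% | 13.5% | 27.1% | 42.4% |
| Either test, ρ = 0 | 6.1% | 6.9% | 7.9% | 8.6% |

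Intention-to-treat stayed at 4.6–5.4%. As-treated alone with ρ = 0 was 4.8–5.3%. The false difference was 0.1–0.4 points for ρ = 0.3 and 0.2–0.7 for ρ = 0.5.

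A larger trial makes it worse. From 10% non-use with ρ = 0.3 to 30% with ρ = 0.5, as-treated error runs from 6.6% to 26.7% at 30 per arm and from 11.5% to 73.0% at 100 per arm.

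If better-balanced patients stop instead, the sign reverses at 50 per arm: error 12.4% and −0.33 points (20% non-use, ρ = 0.3), or 42.7% and −0.70 points (30%, ρ = 0.5).

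**4. A different non-use model.** Non-use followed a logistic model with log-odds rising by 0.5 or 1.0 per SD of poorer balance (2,000 runs per setting). At 50 per arm and 20% non-use at average balance, as-treated error was 12.8% or 35.2%, against 5.0% and 5.2% for intention-to-treat. The false differences were 0.32 and 0.66 points. The pattern is the same.

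**5. How often the two verdicts conflict.** Assume a true 1-point benefit in users (before truncation), 50 per arm, 20% non-use and ρ = 0.3.

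| Who stops using the orthotic | As-treated difference | Intention-to-treat difference | Trials where significance differs |
|---|---|---|---|
| Poorer balance | 1.20 | 0.70 | about 42% |
| Unrelated to balance | 0.90 | 0.72 | about 23–25% |
| Better balance | 0.59 | 0.73 | about 24% |

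**The case against.** The strongest reply is that the harm is conditional and the documents supply none of its conditions. At 5% non-use and ρ = 0.3, as-treated error is only about 6%. With non-use unrelated to balance it is 5%, and with full use the two analyses are identical. The 73% is a corner case. A valid intention-to-treat analysis is already planned and is named first, and running both analyses is not itself an error. This is right about size, and the figures should be read as illustrations. It does not supply the missing ranking: word order in a sentence does not make an analysis primary.

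The conflict rates in step 5 do not measure bias. About a quarter of trials conflict even when non-use is unrelated to balance, so only the excess in the first row reflects selection. That is accepted. The table is there to show that conflict would be common enough for a decision rule to matter.

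The telephone questions are clearly not the whole data collection, because baseline demographics and daily walking distance are also analysed and neither is among them. Use may therefore have been recorded. The point that stands is narrower: the documents do not say how.

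As-treated has a conventional meaning, grouping by treatment received. What is missing is the threshold for use, the handling of partial use, and the handling of controls who use a lift.

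Finally, because the text is in the past tense, a ranking added now may be retrospective. That lowers its weight but does not remove the need for it.

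**Conclusion.** The concern holds. The plan tests its primary outcome twice at 0.05, ranks neither test and does not say who counts as treated. As written, an unadjusted comparison of groups formed after randomisation could decide the trial.

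Multiplicity alone is a modest problem: about 6–9% if either test counts and non-use is unrelated to balance. The larger risk is selection. At 50 per arm, 10–30% non-use related to poorer balance takes the as-treated false-positive rate to about 8–18% (latent correlation 0.3) or 14–42% (0.5), while intention-to-treat stays near 5%. These sizes rest on an assumed mean of 7, SD of 2, arm size, non-use rate and strength of association, and on non-users being counted as control. The missing decision rule and definition rest on no assumption. This should be corrected before any conclusion is drawn from the trial.

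**What to change.** Add to Statistical Analysis, in substance: *The primary analysis is the Wilcoxon rank-sum comparison of the balance score by randomised group (intention-to-treat); it alone decides the trial's conclusion.* Then:

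- Label every as-treated result exploratory and not a basis for claiming benefit.
- State how orthotic use is recorded and what counts as treated in each arm, including partial use and controls who use a lift.
- If use was not recorded, omit the as-treated analysis, because its groups cannot be formed reliably.
- If the analyses have already been run, declare the ranking and the definition as post hoc.

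An instrumental-variable estimate of the effect in compliers is optional, as a sensitivity analysis only. It assumes that assignment acts only through use, which is doubtful for a self-rated outcome with no sham or blinding described.

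The cost is a few sentences and no extra patients. The price to the sponsor is that a favourable as-treated p-value can no longer support the conclusion. With intention-to-treat as the sole deciding test, the simulated false-positive rate was 4.0–5.7% across all settings of the logistic model, consistent with 5% given simulation error.
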